Figure 1 provides an overview of the open-label study design. Subjects will be screened and complete a run-in period of at least 14 days before the baseline visit. Eligible subjects will enter a 16-week treatment period with nemolizumab 30 mg administered subcutaneously every 4 weeks, with a loading dose of 60 mg at baseline/Day 1. The final dose of study drug will occur at Week 12 and subjects will complete the treatment period at the Week 16 visit. An 8-week follow-up period is scheduled (Week 24 visit) for subjects who do not rollover into the nemolizumab long-term extension study. Subjects who prematurely discontinue the study before the Week 16 visit have to be followed for 12 weeks after their last dose of study drug.

The schedule of assessments is summarized in Section 7.2. Assessments of PK, safety, and efficacy will be conducted throughout the study. Patient-reported assessments of pruritus, sleep disturbance and the use of topical AD medication for their eczema will be collected daily.

[figure not shown]
An interim analysis is planned after approximately 10 subjects complete the Week 8 visit. The study will attempt to enroll at least 3 subjects with a low body weight (≤ 61 kg) for the interim analysis and approximately 6 total subjects with low body weight for the overall study population, with investigators attempting to enroll subjects at the lower age range (12-14 years old). The interim analysis will assess whether the observed safety and PK data from adolescents are similar to the data obtained in adults, which is the basis for allowing recruitment of adolescent subjects into the planned nemolizumab Phase 3 studies for AD (pivotal and long-term extension protocols).

An Independent Data Monitoring Committee (IDMC) will review and monitor subject safety. The IDMC will provide recommendations on the safety of subjects. Details on the IDMC, including

CONFIDENTIAL Page 11 of 99

the plan of analysis for IDMC outputs, the composition of the IDMC, the procedures, roles, responsibilities and their communications are provided in the IDMC charter.

Figure 1: Study Design (Synopsis)

: Nemolizumab administration

\*: Loading dose (60 mg) at baseline

Abbreviations: BL = Baseline; n = number of subjects; q4w = every 4 weeks; TCS = topical corticosteroid; W = week

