#### Notes:

- a Subjects are required to fast for at least 8 hours before the visit(s).
- b Visit 3 is a single visit occurring between Week 1 to Week 2.
- c For subjects that complete the Week 16 visit and will rollover to the nemolizumab LTE study, the Week 16 visit (Visit 7) will serve as the final study visit. See Section 7.6.1.
- A follow-up visit is required for subjects who discontinue after the Week 16 visit and will not rollover to the nemolizumab LTE study. The follow-up visit should occur 12 weeks after the last study drug injection. See Section 7.6.1.
- e Assessments to be conducted at the unscheduled visit(s) depend on the reason for the visit. See Section 7.6.2.
- Subjects who discontinue before the Week 16 visit should attend an early termination visit and a follow-up/final study visit 12 weeks after the last study drug injection. See Section 7.6.1.

CONFIDENTIAL Page 37 of 99

Galderma Research & Development, LLC Protocol Number: RD.06.SPR.116912 21-JUL-2020 Version 6.0

- g Patient-reported efficacy measurements (ACT and DLQI/cDLQI) should occur before investigator (efficacy and safety) assessments, blood sample collections, and study drug administration.
- h Peak and average pruritus NRS should be recorded by subjects once daily in the evening, beginning ≥ 2 weeks before Day 1.
- Sleep disturbance NRS should be recorded by subjects once daily in the morning, beginning ≥ 2 weeks before Day 1.
- Subjects will be asked to record the response (yes/no) to the following question each evening, "Did you apply the eczema medication your doctor gave you, to your skin today?", beginning ≥ 2 weeks before Day 1. See Section 7.5.8.1.1.
- Subjects with a history of asthma will complete the ACT at each study visit before physical examination and other investigator assessments. Subjects with de novo diagnosed asthma will complete the ACT beginning at the first visit of de novo diagnosis and at all follow-up study visits.
- Subjects aged 17 years or older will complete the DLQI, while subjects aged 12-16 years old will complete the cDLQI.

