The duration of the follow-up period (ie, 12 weeks after the last study drug administration), corresponds to 5 half-lives of nemolizumab: the drug plasma level is expected to be lower than the Limit of Quantification at the end of the study, and the follow-up period is therefore considered adequate to ensure the safety of subjects.

Background therapy including moisturizer and authorized TCS will be used throughout this study. This is in line with the current practice to use topical agents in conjunction with systemic treatment in more severe cases. Background TCS will be started from the screening visit, to ensure disease stability and avoid flares. The potency of TCS selected for this study is clinically justified. A medium potency TCS will be used on the body where considered safe (eg, trunk and extremities), and a low potency TCS will be used in TCS-sensitive areas (eg, face, neck, intertriginous areas). The prescribed background TCS use should be within daily frequency limits according to the product labeling. Background TCS use includes guidelines to adjust usage to disease activity and

CONFIDENTIAL Page 39 of 99

tolerability of the subject, including tapering when signs and symptoms improve, discontinuation when lesions clear, and restarting if signs and symptoms recur.

Rescue therapy including topical and systemic treatment or phototherapy may be provided if judged to be necessary by the investigator.

This study will assess the PK and safety profile of nemolizumab in the adolescent population, in order to allow their subsequent enrolment in planned Phase 3 studies.

Nemolizumab serum concentration will be assessed at baseline, Weeks 1-2, 4, 8, 12, 16 and Week 24 and at any unscheduled visit for safety reasons. Given that the nemolizumab drug supply configuration and preparation are similar to that used in the Phase 2b study involving adult AD subjects, no change is anticipated in the absorption phase (ka). Thus, limited PK assessment will be done during the absorption phase and serial pre-dose PK samples will be collected at steady state.

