3.3. Brief Description

[figure not shown]
This is an open-label, single-group study to evaluate the PK and safety of 30 mg of nemolizumab in adolescent subjects (12 to 17 years of age), with moderate-to-severe AD and associated pruritus. Approximately 20 eligible subjects will be enrolled to receive subcutaneous injections of nemolizumab (30 mg) every 4 weeks over a 16-week treatment period, with a loading dose of 60 mg on Day 1.

Study participation may include a total of 28 weeks for subjects that complete the screening, treatment and follow-up periods. This study includes a 2 to 4-week run-in period followed by a 16-week treatment period. A follow-up visit (Week 24) is scheduled for subjects who will not immediately rollover (within 7 days following the Week 16 visit) into the nemolizumab open-label extension study. Subjects who prematurely discontinue the study before the Week 16 visit have to be followed for 12 weeks after their last dose of study drug.

Subjects will be screened and complete a run-in period of at least 14 days prior to the Baseline visit. Starting on Baseline/Day 1, all eligible subjects will receive nemolizumab administered subcutaneously, in the presence of background TCS therapy. A loading dose of nemolizumab (60 mg) is administered on Day 1, with subsequent nemolizumab dosing of 30 mg occurring every 4 weeks. The final dose of study medication will occur at Week 12 and subjects will complete the treatment period at the Week 16 visit. An 8-week follow-up period is scheduled (Week 24 visit) for subjects who do not immediately rollover (within 7 days following the Week 16 visit) into the nemolizumab open-label extension study. Subjects who prematurely discontinue the study prior to the Week 16 visit have to be followed for 12 weeks after their last dose of study medication.

Assessments of PK, safety, and efficacy will be conducted throughout the study. Subject-reported assessments of pruritus, sleep disturbance and use of topical medication for their eczema will be collected daily.

Figure 1 below shows a description of the Study Design:

: Nemolizumab administration

* : Loading dose (60 mg) at baseline

Abbreviations: BL = Baseline; n = number of subjects; q4w = every 4 weeks; TCS = topical corticosteroid; W =week.

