6.3. Missing Data

The primary method to impute the missing values for the efficacy assessments will be as follows:

Continuous Endpoints: To impute the missing values for efficacy continuous endpoints, Last Observation Carried Forward (LOCF) approach will be used. Only post-baseline visits will be imputed. Screening or Baseline information will not be used for LOCF. As sensitivity analysis, observed case (OC) will be conducted.

Binary Endpoints: All missing values will be treated as a Non-Responder for the binary endpoints. LOCF and OC will be used to impute the missing values as sensitivity analysis.

LOCF and Non-Responder will be performed to all subsequent, scheduled, missing post-baseline assessments. And when impute the missing data using LOCF and Non-Responder, all efficacy data after use the rescue therapy will be considered as missing. There will be no imputations for missing PK and Safety parameters. Imputation rules for missing dates in AEs and medications are described in the corresponding sections.

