All medications (prior and concomitant medications, rescue medications, and background TCS) will be listed on the ITT population.

8. Efficacy

All the efficacy analyses will be based on the ITT population. All efficacy variables will be summarized by visit from baseline unless specified otherwise. For efficacy analysis, unscheduled visit or ET visit data will be considered for by-visit summary.

All efficacy analysis will be performed using LOCF or Non-responder imputation (unless stated otherwise) and also performed with observed cases (OC) as sensitivity analysis (see Section 6.3 for more details). LOCF and Non-responder will be performed at all post-baseline visits up to Week 24.

In LOCF or Non-responder analyses, all efficacy data will be set to missing after rescue medication is used. In OC analyses, all data will be included even if subject has received rescue medication.

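### SAP Section 8 runs LOCF and non-responder imputation to Week 24, a visit that rollover subjects are not due to attend; end both rules at Week 16 and report Week 24 as observed cases

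*SAP*

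**What the plan says.** **Imputation.** SAP Section 8 states: "LOCF and Non-responder will be performed at all post-baseline visits up to Week 24". It applies to efficacy in the ITT population, which includes subjects who later roll over. SAP 6.3 gives the rules. For continuous endpoints, "Last Observation Carried Forward (LOCF) approach will be used. Only post-baseline visits will be imputed". For binary endpoints, "All missing values will be treated as a Non-Responder for the binary endpoints". On scope it adds: "LOCF and Non-Responder will be performed to all subsequent, scheduled, missing post-baseline assessments".

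**Who attends Week 24.** The synopsis of the protocol says: "An 8-week follow-up period is scheduled (Week 24 visit) for subjects who do not rollover into the nemolizumab long-term extension study". SAP 3.3 agrees: "A follow-up visit (Week 24) is scheduled for subjects who will not immediately rollover", and defines immediate rollover as within 7 days of the Week 16 visit. For rollover subjects, note c to the protocol's schedule (Section 7.2) says that "the Week 16 visit (Visit 7) will serve as the final study visit".

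**What Week 24 represents.** The last injection is at Week 12, so Week 24 falls 12 weeks after it. Protocol 7.3.1 says that by then "the drug plasma level is expected to be lower than the Limit of Quantification at the end of the study".

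**Outputs.** The SAP's figure index has efficacy plots for EASI, IGA success, peak and average pruritus NRS, and sleep NRS. The IGA plot uses non-responder imputation and the others use LOCF. None uses observed cases. Observed-case tables are planned alongside the imputed tables.

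**The concern.** A rollover subject's Week 24 assessment is absent by design. The subject has neither dropped out nor failed treatment. The binary rule makes no distinction between these situations, and Section 8 names Week 24 as the end of the imputation horizon.

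The same rollover subject then appears at Week 24 in two ways. In the EASI, BSA, SCORAD and NRS tables the subject keeps the Week 16 value, recorded 4 weeks after a dose. In the IGA non-responder table the subject is a failure. IGA can also disagree with itself, because its LOCF version may carry the subject forward as a success.

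A reader of the Week 24 row or the last point of a curve will tend to take it as evidence of durability or relapse off drug. Part of what is printed there would instead reflect how many subjects entered the extension study.

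**Working it through.** The documents state no figure to reproduce: no rollover rate, and no sample-size or power calculation that bears on this point. What follows is direct arithmetic on assumed inputs.

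**Inputs from the documents**
- N = 20 (approximate planned enrolment).
- Follow-up length: 24 − 16 = 8 weeks. Time since last dose at Week 24: 24 − 12 = 12 weeks. Both agree with the protocol.

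**Assumed inputs**
- Rollovers r = 5, 10 or 15.
- IGA success p16 = 40% at Week 16. Off-drug success p24 at Week 24 = 40%, 20% or 0%.
- Mean EASI change of −60% at Week 16 (m16) and −30% off drug at Week 24 (m24).
- No other missing data, no rescue use, and the same off-drug outcome whether or not a subject rolls over.

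**Formulas for Week 24**
- Share of the row imputed = r / N
- Non-responder success, all N in the denominator = (N − r) × p24 / N
- LOCF success = [r × p16 + (N − r) × p24] / N
- LOCF mean EASI change = [r × m16 + (N − r) × m24] / N

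**Results**

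| Quantity at Week 24 | r = 5 | r = 10 | r = 15 |
|---|---|---|---|
| Share imputed | 25% | 50% | 75% |
| Response maintained (p24 = 40%): non-responder | 30% | 20% | 10% |
| Response maintained: LOCF | 40% | 40% | 40% |
| Response halves (p24 = 20%): non-responder | 15% | 10% | 5% |
| Response halves: LOCF | 25% | 30% | 35% |
| Response lost (p24 = 0%): non-responder | 0% | 0% | 0% |
| Response lost: LOCF | 10% | 20% | 30% |
| EASI change by LOCF (off-drug value −30%) | −37.5% | −45% | −52.5% |

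Two cells worked out: (20 − 15) × 0.40 / 20 = 2/20 = 10%; and [15 × (−60) + 5 × (−30)] / 20 = −1050/20 = −52.5%.

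Each distortion has its own condition. If response is maintained, LOCF gives the right IGA rate and only the non-responder rate is wrong. If response is lost, the non-responder rate is right and only LOCF is wrong. Both are wrong, in opposite directions, in the intermediate case.

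**Denominator.** SAP 8.2 divides by the subjects with an IGA result available at the visit, whereas SAP 6.1 defaults to the full group. Under 8.2 taken literally, the maintained-response example gives (20 − r) × 0.40 / (20 − r) = 40% for every r. That is an observed-case rate under a non-responder label.

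**After the fix.** The Week 24 row has n = 20 − r: 15, 10 or 5. It contains no value imputed because of rollover.

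**The case against.** The strongest counter-argument is textual. Section 8 refers to 6.3 for detail, and 6.3 confines imputation to scheduled assessments. SAP 3.3 and 3.8 use that word for Week 24 only in connection with subjects who do not roll over. On that reading a rollover subject has nothing to impute, and Section 8 merely sets the last visit. This reading is tenable, so the documents do not support saying that the SAP unambiguously orders the imputation. But the SAP never states the exemption, its visit-window table lists Week 24 as an analysis visit without qualification, and Section 8 names Week 24. Two programmers could follow the text and print different results.

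Second, observed-case tables are already planned, and DLQI/cDLQI and medication-free days are not imputed. This covers part of the gap. However, the observed-case analysis also brings back values recorded after rescue, so it differs from the imputed analysis in two respects, and it feeds no figure.

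Third, Week 24 efficacy is not an objective. The dated efficacy endpoints run to Week 16, Protocol 9.4.4 puts efficacy inference there, and Protocol 7.3.1 describes the follow-up as being for safety. This stands and limits the importance of the point.

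A reader might also infer that most of the Week 24 row will be imputed. That needs at least 11 of 20 subjects to roll over (11/20 = 55%), and no rate is given. Whether early enrollees could roll over at all is uncertain, because adolescent entry to the extension depends on the interim analysis.

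**Conclusion.** The point holds as a defect of specification in a descriptive, secondary output. As written, Section 8 lets the Week 24 efficacy row and the figure end points be imputed in proportion to a rollover rate that the documents do not give. Section 6.3 offers a way out but does not take it.

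The size depends on assumptions. The fall from 40% to 30%, 20% or 10% assumes 20 subjects in the denominator, a response that is fully maintained, and 5, 10 or 15 rollovers. With the SAP 8.2 denominator it does not appear.

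A reader might go further and conclude that continuous and binary endpoints must move in opposite directions at Week 24. The documents do not support that as a general statement: LOCF misleads only if disease changes after Week 16, and non-responder imputation only if some response persists off drug. Week 16 results are unaffected in every case.

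**What to change.** - In SAP Sections 8 and 6.3, end LOCF and non-responder imputation at Week 16.
- Report Week 24 as observed cases among subjects for whom the follow-up visit was due, with n shown, and label the row as off-drug follow-up.
- State how values recorded after rescue are handled in that row.
- In the figures, detach the Week 24 point from the LOCF and non-responder lines.
- In SAP 8.2, give the IGA denominator separately for each analysis: all ITT subjects for non-responder imputation, and subjects with a result for observed cases.

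The cost is a few SAP sentences and some footnotes. Protocol 9.3 sets no Week 24 horizon and leaves imputation detail to the SAP. The drawback is a smaller n at Week 24, and a row that describes only subjects who did not roll over. That n is the amount of off-drug data actually due.

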8.1. Eczema Area and Severity Index

Eczema Area and Severity Index (EASI) is a validated measure commonly used in clinical trials and clinical practice to assess the severity and the extent of AD signs. EASI is a composite score ranging from 0 to 72. The severity of erythema, induration/papulation, excoriation, and lichenification will be assessed by the investigator on a scale ranging from 0 to 3 (0: none; 1: mild; 2: moderate; 3: severe) for four body regions (head/neck, trunk, upper limbs, and lower limbs), with half points allowed. In addition, the extent of AD involvement in each of the four body regions (denoted as "Area") will be assessed as a percentage and converted to a score ranging from 0 to 6 (0% no eczema; 1= 1% to < 10% affected; 2 = 10% to < 30% affected; 3 = 30% to < 50% affected; 4 = 50% to < 70% affected; 5 = 70% to < 90% affected; 6 = 90% to 100% affected). With this information an EASI score for each region will be obtained, and an Overall score as the sum of all body region scores. The EASI scores will be derived and recorded in the CRF as described in Table 2.

Table 2: EASI Score calculation

Body region	EASI score
Head/Neck	(Erythema + Induration/Papulation + Excoriation + Lichenification) x Area x 0.1
Upper limbs	(Erythema + Induration/Papulation + Excoriation + Lichenification) x Area x 0.2
Trunk	(Erythema + Induration/Papulation + Excoriation + Lichenification) x Area x 0.3
Lower limbs	(Erythema + Induration/Papulation + Excoriation + Lichenification) x Area x 0.4
EASI Overall	Sum of the above four body region scores

EASI will be summarized descriptively by visit using LOCF and OC. Absolute change and percent changes from baseline will also be included in the analysis.

For the LOCF analysis, the imputation will be performed for the EASI overall imputated score.

Percent change in EASI using LOCF will be displayed graphically.

All EASI data will be listed.

8.2. Investigator Global Assessment

The Investigator Global Assessment (IGA) is a 5-point scale (defined in Table 3) used by the investigator to evaluate the global severity of AD and the clinical response.

Table 3: IGA 5-point scale

Status	Score	Definition	
Clear	0	Minor, residual hypopigmentation/hyperpigmentation, no erythema or induration/papulation, no oozing/crusting.	
Almost clear	1	Trace faint pink erythema, with barely perceptible induration/papulation and no oozing/crusting.	
Mild	2	Faint pink erythema with mild induration/papulation and no oozing/crusting.	
Moderate	3	Pink-red erythema with moderate induration/papulation with or without oozing/crusting.	
Severe	4	Deep or bright red erythema with severe induration/papulation with oozing/crusting.	

IGA score and change from baseline will be summarized by visit using LOCF and OC.

IGA success is defined as 0 (clear) or 1 (almost clear) and at least 2 grade improvement change from baseline. The IGA treatment success rate will be obtained as the ratio between the number of subjects achieving IGA treatment success and the number of subjects with available IGA result at the visit, and will also be summarized by visit from baseline using Non-Responder, LOCF and OC.

Proportion of subjects achieving IGA success using Non-Responder will be displayed graphically.

For the LOCF analysis, the imputation will be performed based on the recorded IGA per visit, and the imputed IGA treatment success rate will be based on the imputed values.

All IGA data will be listed.

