### Phototherapy

Whenever possible, investigators should first use topical medication as rescue therapy, before escalating to systemic therapies. If subjects receive topical treatments or phototherapy as rescue therapy, study drug administration should be continued unless there is a safety concern according to the investigator's judgment. If subjects receive systemic rescue therapy, the study drug administration must be permanently discontinued.

For the purpose of efficacy analysis, subjects receiving any rescue therapies will be considered as treatment failures.

Further, the use of any rescue therapies should be documented in the CRF.

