# 9.3 Imputation of Missing Data

The primary method to impute the missing values for the efficacy assessments will be as follows:

Continuous Endpoints: To impute the missing values for efficacy continuous endpoints, Last Observation Carried Forward (LOCF) approach will be used. In addition, Observed Case (OC) will be carried out as sensitivity analysis.

**Binary Endpoints:** All missing values will be treated as a Non-Responder for the binary endpoints. LOCF and OC will be used as sensitivity analysis to impute the missing values.

Use of Rescue Therapy: All Efficacy Data, Except OC, Will Be Set To Missing After Rescue Medication Is Used. In OC Analysis, No Observed Data After Subject Has Received Rescue Treatment Will Be Excluded.

There will be no imputations for PK, missing laboratory, and vital sign data. Further details on imputation of missing data will be provided in the SAP.

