6.1. General Methods

This section describes analytical analysis issues that relate to all or some of the analytic analysis sections that follow. It describes general guidelines for analysis as well as the following items:

- SAS version 9.4 or higher will be used.
- CCI will be responsible for reporting the demographic, safety, and efficacy data including listings of the administration information for collection of PK and PD samples.
- Unless otherwise specified, summaries will be presented by visit.
- The total number of subjects in the treatment group (N) will be used as the denominator for percentage calculations, unless stated otherwise in the table shell.
- Continuous variables will be summarized using the number of observations (n), mean, standard deviation (SD), median, minimum, and maximum. Categorical variables will be summarized using number of observations (n) and percentages of subjects.
- Subject data listings will be presented with the ITT population for efficacy assessments, with the Safety Population for safety assessments and with the PK population for PK assessments, unless stated otherwise.
- In general, the listings will be sorted by subject number, and assessment date (and time) if applicable.
- Multiple assessments at a given time point (repeat, and unscheduled) will not be included in summary tables unless specified otherwise, but will be included in the listings.

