16.2.5.2. Table Conventions

- Units will be included where available
- If the categories of a parameter are ordered, then all categories between the maximum and
 minimum category are presented in the table, even if n=0 for dose group in a given category that is
 between the minimum and maximum level for that parameter. For example, the frequency
 distribution for symptom severity would appear as:

Severity	N
Rating	
severe	0
moderate	8
mild	3

Where percentages are presented in these tables, zero percentages will not be presented and so counts of 0 will be presented as 0 and not as 0 (0.0).

- If the categories are not ordered (e.g., Medical History, Reasons for Discontinuation from the Study, etc.), then only those categories for which there is at least 1 subject represented are included.
- An Unknown or Missing category are added to each parameter for which information is not available for 1 or more subjects.
- Unless otherwise specified, the estimated mean and median for a set of values are printed out to 1 more significant digit than the original values, and standard deviations are printed out to 2 more significant digits than the original values. The minimum and maximum should report the same significant digits as the original values. For example, for systolic blood pressure:

n	XX
Mean	XXX.X
SD	X.XX
Median	XXX.X
Min	XXX
Max	XXX

- Percentage values are printed to one decimal place, in parentheses with no spaces, one space after the count (e.g., 7 (12.8), 13 (5.4)). Pre-determine how to display values that round down to 0.0. A common convention is to display as '<0.1', or as appropriate with additional decimal places. Unless otherwise noted, for all percentages, the number of subjects in the analysis population for the treatment group who have an observation will be the denominator. Percentages after zero counts should not be displayed and percentages equating to 100% are presented as 100.0.

- Tabular display of data for medical history, prior/concomitant medications, and all tabular displays
 of adverse event data are presented by the body system, treatment class, or SOC. Within the

body system, drug class and SOC, medical history (by preferred term), drugs (by ATC code), and adverse events (by preferred term) are displayed in alphabetically order. If incidence for more than 1 term is identical, they should then be sorted alphabetically. Missing or not calculated descriptive statistics or p-values which cannot be estimated are reported as "-".

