	14.1.2.2	Summary of Major Protocol Deviations	ITT		
		by Site	Population		
14.1.3		Demographic and Baseline			
		Characteristics			
14.1.3.1		Subject Demographic and Baseline			
	1111011	Characteristics	1		
	14.1.3.1.1	Summary of Demographics and	ITT	Yes	Yes
	444040	Baseline Characteristics	Population		\/
	14.1.3.1.2	Summary of Baseline Disease	ITT Population		Yes
14.1.3.2		Characteristics Medical History	Роригация		
14.1.3.2	14.1.3.2.1	-	ITT	Yes	Yes
	14.1.3.2.1	Summary of Medical History	Population	res	res
14.1.3.3		Medical and Surgical Procedures			
	14.1.3.3.1	Summary of Prior Medical and Surgical	ITT	Yes	
		Procedures	Population		
	14.1.3.3.2	Summary of Concomitant Medical and	ITT	Yes	
		Surgical Procedures	Population		
14.1.4		Medications			
	14.1.4.1	Summary of Prior Medications by ATC	ITT	Yes	
	1	level and Preferred Term	Population		
	14.1.4.2	Summary of Concomitant Medications	ITT	Yes	
	1444	by ATC level and Preferred Term	Population	1,,	
	14.1.4.3	Summary of Rescue Medications	ITT	Yes	Yes
		during Treatment Period by ATC level and Preferred Term	Population		
	14.1.4.4	Summary of Rescue Medications	ITT		Yes
		during Follow-up Period by ATC level	Population		
		and Preferred Term			
	14.1.4.5	Summary of Topical Rescue	ITT		
		Medications during Treatment Period	Population		
		by ATC level and Preferred Term			

Header	Table Number	Name	Analysis Population	Interim Analysis	IDMC
	14.1.4.6	Summary of Topical Rescue	ITT		
		Medications during Follow-up Period	Population		
		by ATC level and Preferred Term			
	14.1.4.7	Summary of Background Topical	ITT		
		Corticosteroids (TCS) Dispensation	Population		
14.1.5		Treatment Compliance			
	14.1.5.1	Summary of Exposure to Study Drug	Safety Population	Yes	Yes
14.2.1		Efficacy Data Summary reported on CRF			
14.2.1.1		Eczema Area and Severity Index (EASI)			
	14.2.1.1.1	Summary of Eczema Area and Severity Index (EASI) Score (LOCF)	ITT Population		
	14.2.1.1.2	Summary of Eczema Area and Severity Index (EASI) Score (OC)	ITT Population		
14.2.1.2		Investigator Global Assessment (IGA)			
	14.2.1.2.1	Summary of Subjects Achieving Investigator Global Assessment (IGA) Success (Non-Responder)	ITT Population		
	14.2.1.2.2	Summary of Investigator Global Assessment (IGA) (LOCF)	ITT Population		
	14.2.1.2.3	Summary of Investigator Global Assessment (IGA) (OC)	ITT Population		
14.2.1.3		Body Surface Area (BSA)	·		
	14.2.1.3.1	Summary of Body Surface Area (BSA) of AD Involvement (LOCF)	ITT Population		

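### Read literally, SAP 8.2's single denominator for the IGA success rate takes missing and rescued subjects out of the Week 16 Non-Responder analysis

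*SAP*

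**What the plan says.** **The endpoint rule.** SAP 8.2 gives one formula for the IGA success rate. The numerator is subjects with IGA success. The denominator is the "number of subjects with available IGA result at the visit, and will also be summarized by visit from baseline using Non-Responder", followed by LOCF and OC. For LOCF, the section adds that "the imputed IGA treatment success rate will be based on the imputed values". It has no matching sentence for Non-Responder.

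**The rules for missing data and rescue.**
- Protocol 9.3: "All missing values will be treated as a Non-Responder for the binary endpoints". SAP 6.3 repeats this.
- Protocol 7.5.8.1.2: "For the purpose of efficacy analysis, subjects receiving any rescue therapies will be considered as treatment failures".
- SAP Section 8, opening text: "In LOCF or Non-responder analyses, all efficacy data will be set to missing after rescue medication is used". The OC analysis keeps post-rescue data.

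**The general percentage rules.**
- SAP 6.1 says of the treatment-group total: "N) will be used as the denominator for percentage calculations, unless stated otherwise in the table shell".
- SAP 16.2.5.2 sets a different default base: "Unless otherwise noted, for all percentages, the number of subjects in the analysis population for the treatment group who have an observation".

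**Where the rate appears.** It is reported in Table 14.2.1.2.1, listed in SAP 18 as "Summary of Subjects Achieving Investigator Global Assessment (IGA) Success (Non-Responder"), and in the Non-Responder plot, Figure 14.2.1.2.4. SAP 5.1 assigns efficacy to the ITT population, and Protocol 9.4.4 places primary efficacy inference in ITT at Week 16. SAP 14 declares no change from the protocol's methods.

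**The concern.** Non-responder imputation affects a proportion only if the imputed subjects stay in the denominator. SAP 8.2 is the rule specific to this endpoint, and its denominator is subjects who have an IGA result at the visit. In the Non-Responder analysis a rescued subject's later results have been set to missing. A programmer who follows 8.2 as written would therefore leave out the subjects whom the protocol wants counted as failures.

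Two things are at stake. The reported Week 16 rate would be higher than the protocol's rule gives. The Non-Responder table would also stop being a conservative counterpart to OC: with missing data and no rescue use the two rates are identical, and with rescue use the Non-Responder rate can be the higher one.

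**Working it through.** The documents give no IGA rate, expected missingness or expected rescue use, so there is no plan figure to reproduce. The check is on the rule and on its possible size.

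**Step 1: what an available result means.** Elsewhere the SAP uses the word as the opposite of missing. In 8.5 and 8.6, a week with fewer than four available daily scores gives a missing weekly score. In 10.3, urinalysis percentages are taken over subjects with available data, and 6.3 allows no imputation of safety data. Non-responder imputation assigns a response status, not an IGA score. On the literal reading, an imputed subject therefore has no available IGA result.

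**Step 2: formulas.** Let N be the ITT count, s the Week 16 successes, and k the subjects whose Week 16 IGA is missing or set to missing after rescue.
- Rate under Protocol 9.3 and SAP 6.3: s/N
- Rate under the literal SAP 8.2: s/(N - k)
- Ratio of the second to the first: N/(N - k)

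**Step 3: inputs.** N = 20 is the approximate planned enrolment (Protocol 7.1, SAP 3.3). The values of s and k are assumed.

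**Step 4: results.** The ratio is 20/20 = 1.00, 20/18 = 1.11, 20/16 = 1.25 and 20/14 = 1.43 for k = 0, 2, 4 and 6.

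| Successes | ITT rate, s/20 | k = 0, s/20 | k = 2, s/18 | k = 4, s/16 | k = 6, s/14 |
|---|---|---|---|---|---|
| 4 | 20% | 20% | 22% | 25% | 29% |
| 8 | 40% | 40% | 44% | 50% | 57% |
| 12 | 60% | 60% | 67% | 75% | 86% |

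**Step 5: comparison with OC.** With missing data and no rescue, the OC denominator is also N - k and the numerator is the same, so the literal Non-Responder rate equals the OC rate.

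Now take 8 successes, 2 subjects missing, and 2 rescued subjects seen at Week 16:
- Literal Non-Responder: 8/(20 - 2 - 2) = 50%
- ITT: 8/20 = 40%
- OC: 8/18 = 44%, 9/18 = 50% or 10/18 = 56%, if 0, 1 or 2 of the rescued subjects meet success

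The literal rate exceeds OC in the first of these three cases only.

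**The case against.** The best answer is that the literal reading stops the imputation halfway. It applies the set-to-missing rule in SAP Section 8 but not the next step, in SAP 6.3, which turns a missing value into a non-response. A reading that leaves a named primary method with no effect is not the natural one. SAP 5.1, SAP 6.1 and Protocol 7.5.8.1.2 all favour the full ITT count. The wording of 8.2 can also be taken to describe an observed-data ratio first and the three imputed summaries separately. If an available result means any recorded score, a rescued subject with a recorded IGA would stay in the denominator as well.

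Much of this stands. An ITT denominator is a plausible reading. SAP 6.1 also defers to the table shell, which is not public and may already name the denominator. What the objection does not remove is the conflict: 8.2 is the specific rule, and SAP 16.2.5.2 points back to subjects with an observation.

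Three stronger readings are tempting, and the documents do not support them.
- A reader might infer that the published rate will be inflated. The documents show two incompatible rules, not which one will be programmed.
- A reader might infer from the LOCF sentence in 8.2 that observed-only denominators are intended for Non-Responder. Parallel LOCF sentences in 8.1 and 8.3 to 8.6 only say at what level values are carried forward, so the silence on Non-Responder shows little.
- Because SAP Section 8 imputes up to Week 24, a reader might infer that subjects who roll over at Week 16 become Week 24 failures. SAP 6.3 limits imputation to scheduled assessments, and SAP 3.3 schedules Week 24 only for subjects who do not roll over immediately.

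**Conclusion.** The point holds as an inconsistency that should be resolved before programming. Taken literally, SAP 8.2 with SAP Section 8 gives a Week 16 Non-Responder rate over the wrong set of subjects, contrary to Protocol 9.3, SAP 6.3 and Protocol 7.5.8.1.2.

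With 8 successes in 20, the overstatement would be about 4 points for two missing or rescued subjects and 10 points for four. It is nil if there are none. The success, missing and rescue counts behind these figures are assumptions; only the planned 20 comes from the documents.

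The consequence is modest. IGA success is a secondary endpoint summarised descriptively in a single-group study with no formal powering. No test or comparator depends on it, and the PK and safety results are untouched.

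**What to change.** In SAP 8.2, replace the single denominator with one for each method:

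> *For the Non-Responder analysis the denominator is all ITT subjects, with missing and post-rescue values counted as failures; for LOCF it is subjects with an observed or carried-forward IGA; for OC it is subjects with an observed IGA.*

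In SAP 16.2.5.2, add to the percentage convention: *except where Section 8.2 sets the denominator*. Give the same denominator in a footnote to Table 14.2.1.2.1 and to the Non-Responder plot.

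The cost is one sentence, one clause and matching footnotes. No new data are needed, and the change carries out what Protocol 9.3 already requires. The reported Week 16 rate may be lower than under the literal wording.
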